В	0159	15-Mar-2022	Added walking test or treadmill test to baseline functional status to assess walking distance (section 4.1); added completion of walking test or treadmill test to 6 month and 12 month follow up (section 4.6); added walking test or treadmill test to Table 2 schedule of events. Updated planned enrollment schedule in protocol summary section.		
С	0162	24-Mar-2022	Added stent post-dilatation clarification to use CVT device to section 4.3 "Criteria for Bail-Out Stenting".		
D	0168	28-Apr-2022	Revise Appendix M (angiographic core lab guideline) to include complete distal runoff images		
E	0189	02-Aug-2022	Corrected Appendix F (Schedule of Events) to include Walking/Treadmill Test at 6M/12M follow up. This change reflects the requirements in the body of the protocol and the Schedule of Events in Table 2.		

Confidential Page 6 of 79

PROTOCOL SUMMARY

Investigational Device	CVT Everolimus-coated Percutaneous Transluminal Angioplasty (PTA) Catheter (CVT EVE-PTA Catheter)			
Study Objective	To assess the safety and inhibition of restenosis of the CVT Everolimus-coated PTA Catheter in the treatment of subjects with de-novo occluded/stenotic or re-occluded/restenotic lesions in superficial femoral or popliteal arteries.			
Study Design	Prospective, multi-center, open, single arm study			
Number of Subjects	A total of 75 subjects will be enrolled			
Number of Sites	Up to eight (8) sites in Europe			
Primary Safety Endpoint	Freedom of Major Adverse Event (MAE) rate at 6 months post-procedure, defined as a composite rate of cardiovascular death, index limb amputation and ischemia-driven target lesion revascularization (TLR).			
Primary Effectiveness Endpoint	Patency at 6 months post procedure, defined as freedom from restenosis as determined by duplex ultrasonography (DUS) (peak systolic velocity ratio (PSVR) ≤2.4 or ≤50% stenosis) and freedom from ischemia-driven target lesion revascularization (TLR).			
Secondary Safety Endpoints	• Rate of Major Adverse Event (MAE) rate in hospital and at 30 days, 1-, 2- and 3-years post-procedure, defined as a composite rate of cardiovascular death, index limb amputation and ischemia-driven Target Lesion Revascularization (TLR).			
	 Rate of occurrence of arterial thrombosis of the treated segment. Rate of ipsilateral embolic events of the study limb. Rate of clinically-driven target lesion revascularization at 6, 12, 24 and 36 months. 			
	• Patency rate at 12 months post procedure defined as freedom from clinically driven TLR and duplex ultrasonography detected restenosis (ultrasound peak systolic velocity ratio ≤ 2.4 or stenosis ≤50%)			
	• Rate of vascular access site complication defined as the combined rate of hematoma, AV fistula or a pseudoaneurysm that required intervention, such as surgical repair or transfusion, prolonged hospital stay, or required a new hospital admission.			
	• Lesion success (per device), defined as achievement of a final in-lesion residual diameter stenosis of <50% (by QA), using any device after wire passage through the lesion. Pre- and post-dilatation of the lesion with a non-study device is considered part of assigned device treatment.			

Confidential Page 7 of 79

 Technical success (per device), defined as achievement of a fin lesion residual diameter stenosis of <50% (by QA), using the C Everolimus-coated PTA Catheter without a device malfunction passage through the lesion. Pre- and post-dilatation are considerassigned device treatment. Clinical success (per subject) defined as technical success with occurrence of major adverse events during the procedure. Procedural success (per subject) defined as lesion success with occurrence of major adverse events during procedure. Ankle-Brachial Index (ABI) changes before procedure compared 					
	 ABI at discharge and at 6 and 12 months. Change in WIQ (walking impairment questionnaire) from preintervention at 6 and 12 months follow-up. Change in walking distance from pre-procedure at 6 and 12 months. Change in Rutherford classification grades of chronic limb ischemia from pre-intervention at 6 and 12 months follow-up for the treated limb. 				
Subject Population	Subjects with documented symptomatic occlusion and/or >70% stenosis of the superficial femoral or popliteal (P1 segment) artery.				
Inclusion Criteria	 Study subjects must fulfill the following criteria: Subject must be at least 18 years of age. Subject or his/her legally authorized representative provides written informed consent prior to any clinical investigation related procedure, as approved by the appropriate Ethics Committee of the respective clinical site. Subject must agree to undergo all clinical investigation plan-required follow-up visits and examinations. Subjects with symptomatic leg ischemia, requiring treatment of SFA or popliteal (P1 segment) artery. De novo or restenotic lesion(s) >70% within the SFA and popliteal arteries in a single limb which are ≥3 cm and ≤15 cm in cumulative total length (by visual estimation). Lesion must be at least 2 cm from any stented area. Subject is willing to provide informed consent and comply with the required follow up visits, testing schedule and medication regimen. Successful wire crossing of lesion. Target vessel reference diameter ≥4 mm and ≤6 mm (by visual estimation). Target lesion(s) can be treated with a maximum of two (2) CVT Everolimus-coated PTA Catheters. 				

Confidential Page 8 of 79

	 10. At least one patent (less than 50% stenosis) tibio-peroneal run-off vessel confirmed by baseline angiography or prior MR angiography or CT angiography. 11. Life expectancy >1 year 12. Rutherford classification of 2, 3 or 4 				
Exclusion Criteria	 				
Exclusion Criteria	Subject with any of the following should be excluded: 1. Pregnant or lactating females.				
	2. Co-existing clinically significant aneurismal disease of the abdominal aorta, iliac or popliteal arteries.				
	3. Significant gastrointestinal bleeding or any coagulopathy that would contraindicate the use of anti-platelet therapy.				
	4. Known intolerance to study medications, everolimus or contrast agents.				
	5. Doubts in the willingness or capability of the subject to allow follow-up examinations.				
	6. Subject is actively participating in another investigational device or drug study.				
	7. History of hemorrhagic stroke within 3 months of procedure.				
	8. Previous or planned surgical or interventional procedure within 30 days of index procedure.				
	9. Prior vascular surgery of the target lesion.				
	10. Lesion length is <3 cm or >15 cm or there is no normal proximal arterial segment in which duplex ultrasound velocity ratios can be measured.				
	11. Known inadequate distal outflow.				
	12. Significant inflow disease.				
	13. Acute or sub-acute thrombus in target vessel.				
	14. Use of adjunctive therapies (i.e. laser, atherectomy, cryoplasty, scoring/cutting balloons, brachytherapy, lithotripsy).				
	15. Outflow arteries (distal popliteal, anterior or posterior tibial or peroneal arteries) with significant lesions (≥ 50% stenosis) may not be treated during the same procedure.				
	16. Treatment of the contralateral limb during the same procedure or within 30 days of the study procedure.				
	17. Rutherford classification of 0, 1, 5 or 6				
	18. Presence of prohibitive calcification that precludes adequate PTA treatment.				
	19. Subjects held in custody in an institution by official or court order.				

Confidential Page 9 of 79

Treatment Strategy	 Target lesion pre-dilatation will be performed to determine lesion treatability and prevent the need for stent implantation for treatment of flow limiting dissection. 				
	• In the absence of flow limiting dissection and if no stent has been needed, the target lesion will be treated with the CVT Everolimus-coated Balloon Catheter from healthy-to-healthy segments.				
Planned Schedule	 First subject enrolled: February - 2022 Last subject enrolled: October - 2022 Last subject last contact: November - 2025 				

Confidential Page 10 of 79

1. STUDY OVERVIEW AND RATIONALE

1.1. Study Overview

The CVT-SFA study is a prospective, multi-center, open, single arm study which will include seventy-five (75) subjects at up to eight (8) sites in Europe and will evaluate an everolimus-coated percutaneous transluminal angioplasty (PTA) catheter for the treatment of de-novo occluded/stenotic or re-occluded/restenotic superficial femoral or popliteal arteries.

Study enrollment will be offered to all subjects who are suitable candidates for balloon PTA to correct occlusive or stenotic lesions of the superficial femoral or popliteal P1 segment artery. Subjects who fail to match the inclusion criteria or who present with any of the exclusion criteria should not be included into this study.

To comply with regulatory requirements, subjects will be required to give written informed consent prior to their participation in the study.

1.2. Background and Literature Review

Peripheral artery disease (PAD) is associated to incident cardiovascular morbidity and mortality¹ and would have affected in 2015 about 236 million people aged 25 years and older worldwide; women accounted around 52% of this population.² Total disease prevalence has been estimated at between 3% and 10%, increasing to 15 to 20% in subjects over 70 years.³ Only about 25 percent of affected individuals undergo treatment for the disease.⁴

The most common symptom of PAD is difficulty in walking (intermittent claudication); less common is critical limb ischemia (CLI) which includes severe, persistent rest pain (requiring treatment with analgesics), ulceration or gangrene of the distal extremity. Lower extremity arterial disease can lead to reduced mobility, limb pain, gangrene and amputation, as well as increased mortality^{3, 5, 6, 7} Subjects with PAD generally also present with cardiovascular disease (CVD) which may explain the increased risk of mortality from myocardial infarction (MI) and stroke for these patients,^{6, 8, 9} with mortality rates at five years ranging from approximately 30% to 44%.^{10, 11}

The superficial femoral artery (SFA) is the most commonly diseased artery in the peripheral (lower limb) vasculature. Available therapies for patients with PAD remain controversial. Treatments include watchful waiting, medical management, endovascular treatment and surgical reconstruction.¹²

Medical management comprises risk factor modification (i.e. diabetes control, smoking cessation, hyperlipidemia lowering), exercise therapy, pharmacological therapy. ^{13, 14, 15}

Risk factor modification therapy is recommended to improve claudication and decrease the morbidity and mortality associated with the progression of PAD. Exercise therapy can produce clinical improvements in walking ability and reductions in claudication pain. ¹⁹⁻²¹ Pharmacological options include antiplatelet and anticoagulant therapies. ^{16, 17, 18}

Surgery is typically reserved for subjects with CLI and is associated with risks such as wound complication, death, MI, infection and leg edema. 18, 23 Patency rates for surgical

Confidential Page 11 of 79

revascularization of the lower extremities have been reported to be 23-74%. 18, 23, 24

During the past decade, endovascular therapy has become the primary therapy in SFA interventions.²⁵

Multiple studies have been published reporting on the short and long-term results of percutaneous angioplasty interventions and/or stenting for PAD. ²⁶⁻⁴⁶ Patency rates were reported to range between 29-93%. ²⁶⁻⁴⁶ A meta-analysis of percutaneous angioplasty with provisional stenting compared to stenting alone for treatment of SFA lesions showed similar rates of target vessel revascularization, making both reasonable choices as endovascular treatments. ⁴⁷

However, restenosis remains as a major limitation of the clinical usefulness of PTA and stenting. Poor long-term results, especially after the treatment of longer lesions in the femoropopliteal region, were reported.⁴⁸⁻⁵⁹

The local application of anti-proliferative drugs (e.g., sirolimus, zotarolimus, everolimus, paclitaxel) for prevention of restenosis in coronary arteries via a stent delivery system has shown that these therapies successfully inhibit or reduce restenosis. 60-74 The use of drug-eluting stents in the superficial femoral and proximal popliteal arteries had promising early results that have not been sustained over the long-term.

The SIROCCO I and SIROCCO II trials evaluated the local application of sirolimus for prevention of restenosis in the superficial femoral artery in 95 subjects comparing use of an uncoated nitinol stent to a drug-coated nitinol self-expanding stent. At 24 months there were no significant differences in ABI or in-stent restenosis as measured by peak systolic velocity ratio using duplex ultrasound. Both groups showed an improvement in Rutherford classification post procedure which was sustained over 24 months. ^{75, 76}

Since the mid-2010s, drug-coated balloons (DCBs) have emerged as the first-line treatment option of obstructive SFA disease. These devices are essentially coated with paclitaxel. However, after promising results of several randomized controlled trials of paclitaxel-coated balloons (PCBs)⁷⁷⁻¹⁰⁰, a meta-analysis of randomized controlled trials published in December 2018 by Katsanos et. al. identified an increased risk of late mortality at 2 years and beyond for patients treated with paclitaxel-coated devices compared to patients treated with uncoated devices¹⁰². Consequently, and further to its meta-analysis of long-term follow-up data from premarket trials, FDA made recommendations in August 2019 on the potential late mortality signal after treatment with paclitaxel-eluting devices in the femoropopliteal artery.¹⁰¹ In June 2020, the French Competent Authority, ANSM (Agence Nationale de Sécurité du Medicament et des Produits de Santé) ¹⁰³, the German Authority BFARM (Bundesinstitut für Arzneimittel und Medizinprodukte) requested all manufacturers to add a warning and clinical summary related to the meta-analysis data to European IFUs.¹⁰⁴

In February 2021, the UK Competent Authority issued a similar statement recommending to not use paclitaxel drug-coated balloons (DCBs) or drug-eluting stents (DESs) in the routine treatment of patients with intermittent claudication, as the mortality risk generally outweighs the benefits.¹⁰⁵

Confidential Page 12 of 79

1.3. Study Rationale

Whereas the concerning long-term outcomes of paclitaxel-coated PTA catheters have led to controversy in the interventional vascular community, CVT has developed an possible catheter-based treatment alternative by combining 1) a proven percutaneous transluminal angioplasty (PTA) balloon catheter designed to treat lesions within the peripheral vasculature with 2) a drug coating using a proven drug, everolimus, as the active pharmaceutical agent to benefit from the proven long history of safety and efficacy of the use of this drug for coronary applications.

Everolimus [40-O-(2-hydroxyethyl)-rapamycin], is a semisynthetic macrolide immunosuppressant, which is in the same family as rapamycin (i.e., the "limus family of drugs") that inhibits mammalian target of rapamycin, and it is known to exert much higher interaction with rapamycin complex 2 leading to a blockage of protein synthesis. This interaction stops cell cycle progression, inhibits smooth muscle cell proliferation and reduces stent restenosis. In addition, everolimus has higher bioavailability and a shorter half-life than sirolimus, then it reduces vascular inflammation and stimulates rapid endothelialization¹.

Everolimus is a drug used worldwide in drug-eluting stents (DES) and is considered the percutaneous treatment of choice for coronary artery disease (CAD). The safety profile of everolimus-eluting stents is well established and safer than paclitaxel-eluting stents in long-term clinical follow-ups².

Use of everolimus, a drug with an excellent safety profile and a very long proven history for cardiovascular use, with a proven PTA catheter was demonstrated by CVT in series of pre-clinical evaluations in the swine model. Extensive bench and pre-clinical studies have demonstrated that the CVT Everolimus-coated PTA Catheter is safe for its intended use with no adverse reactions associated to drug delivery for the treated vessel segment up to 30 days post-treatment in the animal model. The presence of everolimus in the vessel up to 30 days post-procedure, as demonstrated in pharmacokinetics studies, is associated with the possibility of prevention of a restenostic reaction in the treated vessel, characterized by signs of drug effect in the histopathology studies at that time point in the animal model.

The present trial will confirm the positive evaluations garnered to date in pre-clinical studies of the CVT Everolimus- coated PTA Catheter for its intended use of treating subjects with lesions in the SFA or popliteal (P1 segment) arteries.

2. DESCRIPTION OF THE STUDY DEVICE

The Chansu Vascular Technologies (CVT) Everolimus-coated PTA Catheter is an angioplasty

Confidential Page 13 of 79

¹ Trimukhe R, Vani P, Patel A, Salgotra V. Safety and performance of the EverProTM everolimus-eluting coronary stent system with biodegradable polymer in a real-world scenario. World J Cardiol. 2020;12(12):615-625. doi:10.4330/wjc.v12.i12.615

catheter designed to facilitate percutaneous treatment of subjects with documented symptomatic occlusion and/or >70% stenosis of the SFA or popliteal (P1 segment) artery.

The CVT Everolimus-coated PTA Catheter is comprised of two main components:

- 1) A CE-marked, commercially-available PTA balloon catheter (Ebony® 0.018" OTW PTA Balloon Catheter, Natec Medical Ltd. Reduit 72201, Mauritius) designed to treat peripheral vascular artery lesions. The PTA catheters are also previously cleared by FDA for peripheral (PTA) angioplasty indications (FDA classification LIT, K143041).
- 2) A drug coating comprised of an approved, commercially-available active pharmaceutical agent (API) mixed with an approved commercially-available excipient. The active pharmaceutical agent is the drug everolimus, in crystalline form, and it is applied onto the balloon using a glycerol ester excipient. Everolimus, like sirolimus, is an mTOR inhibitor drug with cytostatic properties. Everolimus is currently used in CE mark and FDA approved coronary drug-eluting stents [Promus (Boston Scientific), Xience (Abbott Vascular), Synergy (Boston Scientific)].

2.1. Basic Catheter Specifications

• Guidewire: 0.018"

• Sheath Compatibility: 6 French or greater

• Shaft length: 120 cm

The product size offerings and total dose content for the CVT Everolimus-coated PTA Catheter are listed in **Table 1**. The available sizes are 4.0, 5.0 and 6.0mm diameters and balloon lengths 40, 80 and 120mm. The nominal drug dose on all sizes is $3.0 \mu g/mm^2$.

Table 1. CVT Everolimus-coated PTA Catheter Size Matrix and Total Drug Content

Balloon Diameter	Balloon Length (mm) and Total Drug Content (μg)					
(mm)	40	80	120			
4.0	1508	3016	4524			
5.0	1885	3770	5655			
6.0	2262	4524	6786			

2.2. Indication

The CVT Everolimus-coated PTA Catheter is intended for the treatment of patients with denovo or post-PTA occluded/stenotic or re-occluded/ restenotic lesions (excluding in-stent lesions) ≤150mm in length in femoropopliteal arteries with reference vessel diameters of 4-6mm to establish blood flow and to maintain vessel patency.

For additional information, refer to the Instructions for Use provided as **Appendix E**.

Confidential Page 14 of 79

3. STUDY DESIGN

The CVT-SFA Trial investigates the inhibition of restenosis using the CVT Everolimus-coated PTA Catheter in the treatment of de-novo occluded/ stenotic or re-occluded/ restenotic superficial femoral or popliteal arteries. The clinical study will be a prospective, multi-center, open, single-arm study.

Each subject will be followed for at least 3 years (36 months) after treatment. All subjects will have a follow-up contact or an optional office/hospital/clinic visit at 30 days. A follow-up office/hospital/clinic visit will occur at 6 and 12 months and a follow up phone call will occur at 24 and 36 months.

To participate in this study, the site will need the resources necessary for conventional vascular surgery as well as for fluoroscopy-guided catheter-based procedures with high quality imaging.

The study participation flow chart is provided in Figure 1.

[figure not shown]

Figure 1. CVT-SFA Study Participation Flow Chart

3.1. Primary Endpoints

Primary Safety Endpoint

The primary safety endpoint for the study is freedom of major adverse event (MAE) rate at 6 months post-procedure, defined as a composite rate of cardiovascular death, index limb amputation and ischemia-driven target lesion revascularization (TLR).

Confidential Page 15 of 79

Primary Effectiveness Endpoint

The primary effectiveness endpoint for the study is patency at 6 months post-procedure, defined as freedom from restenosis as determined by duplex ultrasonography (DUS) (peak systolic velocity ratio (PSVR) \leq 2.4 or restenosis \leq 50%) within 6 months and freedom from ischemia-driven target lesion revascularization (TLR).

Restenosis is determined by either PSVR >2.4, as assessed by an independent DUS core laboratory, or >50% stenosis, as assessed by an independent angiographic core laboratory in the event an angiogram has been recorded.

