3.2. Secondary Endpoints

The following endpoints will be also evaluated as secondary endpoints:

- Rate of Major Adverse Event (MAE) Rate in hospital and at 30 days, 1, 2 and 3 years post-procedure, defined as a composite rate of cardiovascular death, index limb amputation and ischemia-driven Target Lesion Revascularization (TLR).
- Rate of occurrence of arterial thrombosis of the treated segment.
- Rate of ipsilateral embolic events of the study limb.
- Rate of clinically-driven target lesion revascularization at 6, 12, 24 and 36 months.
- Patency rate at 12 months post-procedure, defined as freedom from clinically driven TLR and duplex ultrasonography restenosis (ultrasound peak systolic velocity ratio ≤ 2.4 or stenosis ≤50%)
- Rate of vascular access site complication defined as the combined rate of hematoma, AV fistula or a pseudoaneurysm that required intervention, such as surgical repair or transfusion, prolonged hospital stay or required a new hospital admission.
- Lesion success (per device), defined as achievement of a final in-lesion residual diameter stenosis of <50% (by QA), using any device after wire passage through the lesion. Pre- and post-dilatation of the lesion with a non-study device is considered part of assigned device treatment.
- Technical success (per device), defined as achievement of a final in-lesion residual diameter stenosis of <50% (by QA), using the CVT Everolimus-coated PTA Catheter without a device malfunction after wire passage through the lesion. Preand post-dilatation are considered part of assigned device treatment.
- Clinical success (per subject), defined as technical success without the occurrence of major adverse events during the procedure.
- Procedural success (per subject), defined as lesion success without the occurrence of major adverse events during procedure.
- Ankle-Brachial Index (ABI) changes before procedure compared with ABI at discharge and at 6 and 12 months.

Confidential Page 16 of 79

- Change in WIQ (walking impairment questionnaire) from pre-intervention at 6 and 12-months follow-up.
- Change in walking distance from pre-procedure at 6 and 12 months.
- Change in Rutherford classification grades of chronic limb ischemia from preintervention at 6 and 12-months follow-up for the treated limb.

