The principle of including outcomes of all patients in the analysis who are enrolled into the clinical trial/investigation, regardless of the treatment actually received.

Late Lumen Loss (LLL)

Calculated as Minimum Lumen Diameter (MLD) post-procedure – MLD at follow-up

Mean in-lesion Late Loss will also be measured: (Mean In-lesion MLD, post-procedure) – (Mean In-lesion MLD at follow-up)

Lead Principal Investigator

A physician-specialist, related to the study, who is responsible for the overall conduct of the trial at all sites.

Major Adverse Event (MAE)

A composite rate of cardiovascular death, index limb amputation and ischemia-driven Target Lesion Revascularization (TLR).

Minimum Lumen Diameter (MLD)

The average of two orthogonal views (when possible) of the narrowest point within the area of assessment – in lesion, in stent or in segment. MLD is visually estimated during angiography by the Investigator; it is measured during QA by the Angiographic Core Lab.

Multilevel Disease

Presence of obstructive lesions at more than one level in the same extremity as the treatment lesion.

Myocardial Infarction (MI)

Q-wave MI (QMI) - Development of new pathological Q-waves in 2 or more contiguous leads (according to the Minnesota code) with or without post-procedure creatine kinase (CK) or CK-MB levels elevated above normal.

Occlusion

Incomplete vessel opacification distal to the lesion or if the distal vessel fills via collateral circulation.

Chronic Occlusion:

An occlusion presumed to have been present for at least 1 month prior to the procedure.

Total Occlusion:

An occlusion with no ante grade filling of contrast to the distal segment.

Patency Rate

Patency rate defined as freedom from clinically-driven TLR and from Duplex ultrasound or angiographic stenosis >50% at 6, 12, and 24 months.

Percent Diameter Stenosis

Confidential Page 58 of 79

The value calculated as 100 * (1 - MLD/RVD) using the mean values from two orthogonal views (when possible) by QA.

Popliteal Artery

Defined as the vessel located between Hunter's canal and the trifurcation of the anterior tibial, posterior tibial and peroneal arteries.

Primary Investigator

A physician responsible for conducting the clinical trial at each investigational site, which is responsible for the overall conduct of the trial at their site and compliance with protocol.

Reference Vessel Diameter (RVD)

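### The 6-month patency rule and the restenosis rule in Section 3.1 are not complements, so a subject with PSVR ≤2.4 but >50% stenosis on an unscheduled angiogram is classified both ways

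*Combined protocol and SAP*

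**What the plan says.** The documents state the patency or restenosis rule in several places.

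- **Protocol Summary, primary effectiveness endpoint:** "freedom from restenosis as determined by duplex ultrasonography (DUS) (peak systolic velocity ratio (PSVR) ≤2.4 or ≤50% stenosis", together with freedom from ischemia-driven TLR.
- **Section 3.1, first paragraph on effectiveness:** "patency at 6 months post-procedure, defined as freedom from restenosis as determined by duplex ultrasonography (DUS", followed by the same pair of thresholds joined by *or*, within 6 months.
- **Section 3.1, next paragraph:** "Restenosis is determined by either PSVR >2.4, as assessed by an independent DUS core laboratory, or >50% stenosis", the stenosis limb being "as assessed by an independent angiographic core laboratory in the event an angiogram has been recorded".
- **Section 3.2, 12-month patency:** freedom from clinically driven TLR and from "duplex ultrasonography restenosis (ultrasound peak systolic velocity ratio ≤ 2.4 or stenosis ≤50" percent). The Protocol Summary repeats this entry in near-identical words. Neither place carries the restenosis paragraph of 3.1.
- **Appendix B, Patency Rate:** "Patency rate defined as freedom from clinically-driven TLR and from Duplex ultrasound or angiographic stenosis >50% at 6, 12, and 24 months". This has no PSVR cut-off.
- **Appendix B, Binary Restenosis and Restenosis:** 50% or more, by angiography only.

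On data collection, Table 2 and Appendix F schedule duplex at 6 and 12 months but no angiogram after the index procedure. The examiner worksheet in Appendix I has fields for velocities in cm/sec and none for percent stenosis. Section 4.6 collects information on repeat angiography, and Appendix M gives instructions for angiograms taken for clinical events.

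**The concern.** The patency parenthesis joins its two good results with *or*, so one good result is enough. The restenosis paragraph joins its two bad results with *or*, so one bad result is enough. Both cannot define the same binary endpoint when the two measurements disagree, and no section gives an order of precedence or a rule for discordant readings.

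This is the numerator of the primary effectiveness endpoint in an open, single-arm trial set against a fixed 65% OPC. The affected subjects are those who had an event angiogram, which is where failure is suspected. Because the restenosis paragraph appears only under the primary endpoints, the 6-month and 12-month patency rates could also end up on different rules.

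**Working it through.** **Inputs.** OPC 65%, assumed patency 65% + 15 points = 80%, one-sided α 0.025, about 68 evaluable, worked example 55/68, stated power 78% (all Section 6.3); Clopper-Pearson interval (Section 6.4).

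**Step 1: the plan's own figures.**
- Power, normal approximation: Φ[(0.15 − 1.96·√(0.65·0.35/68)) / √(0.80·0.20/68)] = Φ(0.755) = 77.5%, against 78% stated. This confirms the inputs.
- Example: 55/68 = 80.9%, printed as 81%. The printed interval of 71.5% to 90.2% is the Wald interval, 0.809 ± 1.96·√(0.809·0.191/68) = 0.809 ± 0.093. The planned Clopper-Pearson interval for 55/68 is 69.5% to 89.4%, and it is used below.

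**Step 2: the logic.** Leave TLR aside and write the two rules of Section 3.1 as:
- P (parenthesis, patent) = PSVR ≤2.4 **or** stenosis ≤50%.
- R (next paragraph, restenotic) = PSVR >2.4 **or** (angiogram recorded and stenosis >50%).

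The complement of R is PSVR ≤2.4 **and** (no angiogram, or stenosis ≤50%). That is not P.

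| PSVR | Stenosis | By P | By R |
|---|---|---|---|
| ≤2.4 | no angiogram | patent | not restenotic |
| ≤2.4 | ≤50% | patent | not restenotic |
| ≤2.4 | >50%, angiogram | patent | **restenotic** |
| >2.4 | ≤50% | patent only if a duplex percent stenosis exists | restenotic |
| >2.4 | >50% | not patent | restenotic |

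The third row conflicts on any literal reading. The fourth is uncertain and is taken up under the objection.

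**Step 3: direction.** Every subject who is patent by the complement of R has PSVR ≤2.4 and so is patent by P. The reverse is not true. Choosing P over R can therefore raise the patency count or leave it unchanged, never lower it.

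**Step 4: who can be in the third row.** The subject needs an unscheduled angiogram showing >50% stenosis, a PSVR ≤2.4, and no TLR that already fails the endpoint. The TLR component need not catch everyone. Appendix B does not define ischemia-driven TLR. Its clinically indicated TLR requires Rutherford worsening by more than 2 categories, or to category 5 or 6. If that standard were applied, a subject could be re-treated without meeting it and then show PSVR ≤2.4 at the 6-month duplex.

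**Step 5: scale.** Each reclassified subject moves the rate by 1/68 = 1.5 points. The limits are Beta quantiles: lower = Beta(0.025; x, 68−x+1), upper = Beta(0.975; x+1, 68−x). The number d of discordant subjects among the 55 is assumed, because the documents give none.

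| d | Patent | Rate | Exact 95% CI |
|---|---|---|---|
| 0 | 55/68 | 80.9% | 69.5% to 89.4% |
| 1 | 54/68 | 79.4% | 67.9% to 88.3% |
| 2 | 53/68 | 77.9% | 66.2% to 87.1% |
| 3 | 52/68 | 76.5% | 64.6% to 85.9% |

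The lower limit crosses 65% between two and three subjects (3/68 = 4.4%).

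**The case against.** The best defence is that Section 3.1 already supplies the working rule. Patency is freedom from restenosis, and the next paragraph says how restenosis is determined, naming the assessor, the modality and the condition for each limb. On that reading the parenthesis is loose shorthand for the thresholds, and the conflicting subject is restenotic. This is the natural reading and probably the intent. But the text does not say that it prevails, and the paragraph is absent from the Summary and from the 12-month endpoint.

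The second defence is reach. With no follow-up angiogram scheduled, most subjects will have PSVR alone and be classified the same way by both rules. That stands, and it limits the point.

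Three stronger readings are tempting and not supported:
- *Both discordant patterns are clearly double-classified.* The parenthesis qualifies a duplex determination, so PSVR >2.4 with an angiographic stenosis of, say, 40% does not plainly satisfy it. A duplex percent stenosis would be needed, and the worksheet has no field for one. The core laboratory might derive one, but the documents do not say so.
- *The 12-month endpoint is governed only by the permissive wording.* The Appendix B patency entry also covers 12 months, and there a stenosis above 50% by either modality is a failure. It does not settle the matter, because it drops PSVR, and the neighbouring restenosis entries put exactly 50% on the other side of the line.
- *The 55/68 example fails.* Three discordant subjects is a tipping point, not a forecast, and Sections 6.1 and 6.3 say that statistical significance is neither necessary nor sufficient here. That emphasis on estimation does, however, make an unambiguous numerator more useful.

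**Conclusion.** The inconsistency is real and sits in the definition of a primary endpoint. One pattern, PSVR ≤2.4 with >50% stenosis on an unscheduled angiogram and no qualifying TLR, is patent by one paragraph of Section 3.1 and restenotic by the next. The Summary, Section 3.2 and Appendix B do not resolve it.

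The expected effect is probably small. Its direction is known: the permissive reading can only raise patency. Its size is not known. An upward bias is possible but not demonstrated. Over an assumed 0 to 3 discordant subjects in the plan's example, the exact lower limit runs from 69.5% to 64.6%. This should be corrected before the 6-month analysis, as a matter of definition; it does not show that the design or its OPC comparison is unsound.

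**What to change.** In the Protocol Summary (both the 6-month and the 12-month patency entries), Section 3.1 and Section 3.2, state patency as: PSVR ≤2.4 by the DUS core laboratory and, where an angiogram was recorded, stenosis ≤50% by the angiographic core laboratory. That is the exact complement of the existing restenosis sentence in 3.1. Replacing *or* with *and* alone would not do, because the parenthesis is tied to duplex and does not carry the condition on an angiogram having been recorded.

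Apply the same rule at 6 and 12 months. Bring the Appendix B entries for Patency Rate, Binary Restenosis and Restenosis into line with it, including the PSVR cut-off and the treatment of exactly 50%. The TLR component is also worded differently at the two times (ischemia-driven at 6 months, clinically driven at 12) and is best reconciled in the same edit.

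The cost is wording only, with no new measurements or visits. Reported patency may be slightly less favourable than under the permissive reading.
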